communication, make changes to clinic work flow, and ensure patients and caregivers are able to follow recommended corrective actions. In order to translate MPI to pediatric practices, we will enhance it in several ways: (1) use clinic rather than research staff to facilitate assessment for prompts at every visit; (2) ensure prompting for guideline-based care for all children ages 2-12 with persistent or uncontrolled asthma, rather than just a research sample; (3) routinely deliver prompts to the provider via EHR; (4) offer telephone-based care coordination, education and support to children with the highest morbidity via a dedicated Outreach Worker (OW) to ensure recommendations are followed; and (5) provide practice-level supports (e.g. clinic champions, on-going performance feedback and participatory problem solving) to promote full adoption of guidelines. The enhanced MPI program (**eMPI**) consists of innovative multi-level and team-based strategies to enable providers to effectively and efficiently adopt asthma care guidelines.

We will conduct a cluster randomized trial comparing eMPI to enhanced usual care (eUC) in 22 Bronx practices serving over 5,000 children ages 2-12 years with persistent or uncontrolled asthma. Eleven eUC practices will receive guideline information and assess children's asthma severity and control, but active intervention components will not be provided. Practices will join the study in 4 waves over 4 years (4-6 practices per year). Including attendings and residents we anticipate enrolling an estimated 200 providers into the study.

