medication use, exposure to triggers, and specific tailored recommendations for guideline-based preventive care (e.g. for persistent asthma without controller medication, the recommendation on the prompt will include starting controller medication). For children with poor control despite being on controller medications, recommendation will include evaluation of inhaler technique and medication adherence, treatment and referral for evaluation of co-morbidities (e.g., referral to the Asthma Center for allergy and pulmonology consultations), "step-up" of medications, evaluation and counseling on triggers, and outreach worker referral (See below). The prompt will also include a recommendation for the provider to establish treatment goals with the patient and inquire about any caregiver's concerns. The prompt for the provider will be seen on the computer screen in EPIC EHR at the time of the visit allowing provider to check off the guideline-based recommended items discussed during the visit. The *caregiver prompt* will include immediate feedback on child's asthma severity/control with personally tailored information highlighting caregiver's goals and concerns. The prompt will include simplified recommendations for preventive care issues to discuss with the provider during the visit (e.g., to discuss triggers, medication concerns, need for asthma action plan (AAP) and medication administration form (MAF) for school). AAP and MAF are embedded into EPIC EHR patient chart and can be printed and given to patient to take home or to school. The caregiver prompt is based on the guideline recommendation to promote joint discussions about treatment plan and goals and will be printed for caregiver to bring to the visit. *Outreach worker* (OW)-delivered telephone-based care coordination and support will be provided by the bilingual (English/Spanish) OWs, lay people from the community who have asthma or a child with well-controlled asthma. OWs will become a practice-based resource. OWs will provide telephone-based care coordination, education and support to children who are already on controller medication but still have uncontrolled asthma and other barriers to guideline-based care (e.g., unable to fill a prescription, loss of medical insurance, poor medication adherence, gaps in caregiver knowledge despite provider education). The decision to refer family to OW service will be based on provider's assessment at any office visit. Providers will be prompted to make OW referrals for children with uncontrolled asthma as part of the guideline-based care. We estimate that 20% of children in each intervention practice will be referred to the OW. Providers will have a referral mechanism embedded within EHR to refer patients to the OW with suggestions on which children should be referred. *OW training:* OWs will be trained (4-weeks) by the PI ([name]) and Co-Is ([name], [name]) using evidence-based guidelines on asthma self-management skills, proper inhaler technique, triggers, medication use, goal setting and problem solving. The PI will oversee OWs with bi-weekly (and more often if needed) meetings to discuss cases/concerns and will listen to 20% of the recorded telephone calls to ensure the OWs deliver the sessions as intended. *OWs role:* OWs will help facilitate implementation of the guideline-based care prescribed by provider at the office visit. If referred to the OW at the initial visit, the first OW telephone call with the child's caregiver will occur within 2 weeks after the initial visit to determine any care coordination needs (e.g., assistance scheduling specialty appointments, inability to fill prescriptions) and then monthly, starting at 1-month post-initial visit for 6 months. If referred at the follow-up office visit, the same

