#### **Clinic-Level Variables**

The **primary outcome** is a clinic-level variable measured by the proportion of visits with  $\geq 1$  guideline-based corrective actions. To calculate this proportion, the denominator will include only the visits by patients aged 2-12 years with persistent or uncontrolled asthma at the time of visit. We will obtain these data from the EHR at baseline, monthly during the initiation phase (to provide feedback to eMPI practices) and every 3 months thereafter for 24 months. Corrective actions include: (1) prescription of a new preventive asthma medication; (2) increase in dose of a preventive medication (for children already on preventive medication); (3) evaluation and counseling regarding triggers; (4) treatment of co-morbid conditions (e.g., sinusitis, allergic rhinitis, obesity); (5) referral to an allergy or pulmonary specialist. We will consider children receiving any of these guideline-based preventive care measures during the visit as having a corrective action (as not all actions may be necessary for each patient), and also will consider each component of preventive care separately. We collected prospective data on most items included in the corrective action definition in our prior work. Additional corrective actions include recommendations for a follow-up visit specifically to discuss asthma, referrals made to OW, and provision of an asthma action plan or school medication administration form.

**Covariate:** Practice characteristics will include practice size (small, medium, large), practice type (hospital-based practice, Federally Qualified Health Center, neighborhood health center), and patient mix (pediatrics, adult/pediatrics), involvement of support staff in the delivery of preventive asthma care, practice-level changes (e.g., new asthma-related initiatives in the practice). We will obtain this information from the existing database of practices and from interviews with the physician champion and office administrator at each practice.

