### **Aim 1. To test the impact of eMPI on provider adoption of asthma management guidelines.**

The **primary outcome** is a clinic-level variable measured by the ratio of number of visits with  $\geq 1$  guideline-based corrective actions to the number of visits by patients aged 2-12 years with persistent or uncontrolled asthma at the time of visit. The **primary null hypothesis** is that there is no difference between eMPI and eUC clinics in the mean proportion of visits where the necessary corrective actions were taken. To test this null hypothesis, we will use a matched-pairs randomization (or permutation test) at the 0.05 two-tailed level of

significance. The permutation test will account for the fact that clinics (rather than providers) are randomized and that the randomization will be performed within clinic pairs. Each pair of clinics will produce a matched difference in the proportions of corrective actions, and under  $H_0$  the randomization can be viewed as attaching a random plus or minus sign. Thus there will be  $2^{11} = 2,048$  possible signed permutations, allowing a two-tailed p-value as significant as  $2/2,048 < 0.001$  (if all 11 pairs show a greater proportion of corrective actions taken by the eMPI practices). Assuming no important practice characteristics are significantly out of balance (at two-tailed  $p < 0.01$ ), the permutation test will comprise the primary analysis. If any important clinic characteristics are significantly imbalanced at  $p < 0.01$ , we will adjust for such variables in a linear regression model and report the adjusted intervention coefficient as the primary result. We will also examine for a clinic-size (or provider-type) by intervention interaction. If not significant at the 5% level, the above approach will be used to provide the primary results. If significant, we will attempt to identify factors that affect the primary outcomes and might differ between clinics (or provider types). If including such factors removes the interaction, we will quote the adjusted intervention effect from the model including such factors. If not, we will quote two intervention effects (for large and small clinics) leaving the interaction unresolved.

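### The primary numerator does not say whether outreach-worker referral counts; it is in effect available only in the eMPI arm, so it should be excluded explicitly

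*Combined protocol and SAP*

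**What the plan says.** The Clinic-Level Variables section defines the primary outcome as the proportion of visits with at least one guideline-based corrective action, among visits by children aged 2-12 with persistent or uncontrolled asthma at that visit. It numbers five actions: new preventive medication, increased preventive dose, trigger evaluation and counselling, treatment of co-morbid conditions, and specialist referral. The scoring rule follows: "We will consider children receiving any of these guideline-based preventive care measures during the visit as having a corrective action". After a sentence on earlier data collection, the same paragraph adds: "Additional corrective actions include recommendations for a follow-up visit specifically to discuss asthma, referrals made to OW, and provision of an asthma action plan", and then the school medication form. It does not say whether these additional actions enter the numerator.

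The Aim 1 analysis restates the ratio without listing actions. Its null hypothesis is no difference "in the mean proportion of visits where the necessary corrective actions were taken".

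On the OW, the Background lists among the eMPI enhancements a plan to "offer telephone-based care coordination, education and support to children with the highest morbidity via a dedicated Outreach Worker (OW"), and Table 4 includes OW support as a core element. The eMPI Intervention paragraph says: "Providers will be prompted to make OW referrals for children with uncontrolled asthma as part of the guideline-based care". It also says: "We estimate that 20% of children in each intervention practice will be referred to the OW". The eUC paragraph says that active intervention components are not provided there.

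**The concern.** The outcome counts guideline-based corrective actions. The outcome section labels OW referral a corrective action, and the intervention section calls it part of guideline-based care. An analyst who built the EHR query from those labels could include it and claim to have followed the plan. An analyst who stopped at the five numbered items could claim the same.

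The choice is not neutral between arms. eMPI practices have the OW service, a referral route in the EHR and a prompt to use it. Nothing in the document gives eUC practices an OW. If the item counts, eMPI clinics have a way to score a visit that eUC clinics in effect lack. Part of the arm difference could then arise with identical medication, trigger, co-morbidity and specialist care. The permutation test cannot separate that part. Reporting each component separately, as the plan intends, helps interpretation but leaves the primary test unchanged.

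**Working it through.** **1. Which reading the text supports.**

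- For five actions only: the any-of-these rule comes before OW referral is named. Objective 1 under Study Objectives illustrates the outcome with controller prescription or adjustment and trigger evaluation only. Objective 3 and the Aim 3 analysis place OW referrals among utilization and resources.
- For counting OW referral: the label in the outcome paragraph and the guideline-based-care description in the eMPI Intervention paragraph.
- Not decisive: the Objective 1 illustration also omits co-morbidity treatment and specialist referral, so it is not a complete list. Aim 1 has no list.

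The five-action reading is favoured but not stated.

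**2. Whether OW-only visits can occur.** Only visits with an OW referral and none of the five actions add to the numerator. They are possible. OW support is meant for children already on a controller, with barriers such as "unable to fill a prescription, loss of medical insurance, poor medication adherence, gaps in caregiver knowledge despite provider education", and none of these is one of the five actions. They are probably a minority, because the same prompt for poorly controlled children recommends stepping up "of medications, evaluation and counseling on triggers, and outreach worker referral".

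**3. The plan's own figure.** With 11 pairs, a difference of 0.25 and an SD of paired differences of 0.20, the non-centrality is (0.25/0.20) × √11 = 4.15. Two-sided paired-t power on 10 degrees of freedom is 96.1%, which reproduces the stated figure of more than 95%. The Subjects and Setting section reports 18 participating practices. With 9 pairs the same inputs give 90.6%.

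**4. Referral rate per visit.** Table 1 gives 17,567 visits by 10,109 children with asthma, so visits per child-year = 17,567/10,109 = 1.738. The plan's 20% is per child and has no time base, so two assumptions are shown:

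- one referral per year: 0.20/1.738 = 0.115 per visit;
- one referral per 24 months: 0.20/3.476 = 0.058 per visit.

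**5. Added difference.** With no eUC referrals,

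added difference = referrals per visit × s,

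where s is the share of referral visits with none of the five actions. The documents do not give s.

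**6. Chance of a significant result if nothing else differs between arms.** This is the two-sided 5% paired-t test with SD 0.20 and non-centrality (added difference/0.20) × √pairs. For example, 0.115/0.20 × √11 = 1.91 gives 41%.

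| s | Added difference (points) | 11 pairs | 9 pairs |
|---|---|---|---|
| 10% | 0.6 to 1.2 | about 5% | about 5% |
| 50% | 2.9 to 5.8 | 7% to 14% | 7% to 12% |
| 100% | 5.8 to 11.5 | 14% to 41% | 12% to 33% |

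The last row is the bound under the assumptions in step 4. A simulation of the planned sign-flip test (20,000 trials, normal differences) agrees closely: at 5.8 and 11.5 points it rejects in 14% and 40% with 11 pairs, and in 11% and 32% with 9.

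**7. If eMPI achieves its planned 25 points.** As an example, take s = 25%, the share with none of the five actions if 75% of eMPI visits have one and referral is independent of them. The gain is 0.115 × 0.25 = 2.9 points, so the estimate becomes 27.9. Power moves from 96% to 99% (11 pairs) or from 91% to 95% (9 pairs). This is an illustration and not a limit, since s could be higher.

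**The case against.** The strongest reply is that the definition is already closed. Five actions are numbered, the rule refers to them, and the additional actions come later. The Objective 1 illustration and the utilization lists point the same way. This stands as the more natural reading, but it rests on sentence order: no sentence excludes OW referral, and the paragraph itself calls it a corrective action.

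A second reply is that a referral is a provider's decision and is not the OW service itself. That also stands. A reader might infer that delivering eMPI would automatically score as success, and the documents do not support this. A referral changes the outcome only when none of the five actions was taken.

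Third, zero OW referral in eUC is an inference. The Aim 3 analysis mentions OW referrals when describing utilization in both groups. Still, nothing gives eUC an OW, and active components are withheld there.

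Fourth, the size depends on assumptions. A reader might apply the 20% directly to visits and infer a larger inflation, but the plan states it per child. The Table 1 visit rate covers all children with asthma, whereas the primary denominator is limited to visits with persistent or uncontrolled disease.

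**Conclusion.** The concern holds as an unresolved definition of the primary numerator with a one-directional consequence. It does not show that the planned analysis will count OW referral; the text leans against that. If it is counted, the comparison tilts toward eMPI by the referral rate per visit times an unknown share. That is 0.6 to 1.2 points at a 10% share, 2.9 to 5.8 at 50%, and 5.8 to 11.5 at 100%. These figures assume one referral per referred child per year or per 24 months, 1.74 visits per child-year, and no OW referral in eUC. The rejection probabilities also assume an SD of 0.20 and no other arm difference.

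A reader might infer that the trial could succeed on OW referral alone. The documents do not support that as the likely course: the prompt pairs referral with actions that already count, and the planned effect is 25 points. Modest inflation of the estimate is more likely than a changed decision. The point should still be fixed, because it concerns the primary endpoint and the choice could otherwise be made after the data are seen.

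**What to change.** In Study Objectives (Objective 1), Clinic-Level Variables and the Aim 1 analysis, state that OW referral does not count toward the primary numerator and is reported separately as an eMPI process measure. In the same places, state whether asthma follow-up recommendations, action plans and school medication forms count. The document does not tie these to the OW service; the action plan and school form are embedded in the EHR chart.

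The cost is a change of wording and a matching EHR query. The observed eMPI effect may be slightly smaller than if OW referral were counted.

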#### **Provider-Level Variables**

**Potential Mediators: 1) Provider Competencies:** We will assess a) provider's asthma practices (frequency of assessing patient symptom severity, treatment adherence, and use of guideline-consistent care), and b)

frequency of use of communication and education strategies contained in the Physician Asthma Care Education (PACE) physician survey. **2) Provider/Caregiver Communication:** We will ask providers in all practices to complete a brief survey at the beginning (during initiation) and end of the study (during sustainability phase). The survey is adapted from the PACE assessment and includes questions about asthma care practices and communication with families. The providers will also be asked if they have been involved in other quality improvement or educational efforts on asthma care. Survey link will be sent to providers electronically.

**Covariate:** We will collect data on provider type (MD, PNP, PA), the level of training (resident or attending), specialty (family medicine or pediatrics), and if the visit's provider was the child's primary care provider. We will obtain this information from the chart review, caregiver interview for a subset of patients and provider survey.

### **Patient-Level Variables**

**Clinical/Functional Outcomes** will be collected from caregivers of 512 children (Table 5).

**1. Asthma Symptoms:** We will assess number of symptom-free days (SFDs) (**secondary outcome measure**) at baseline, 3 months to determine short-term effectiveness of the intervention, and at 6, 9, and 12 month follow-up evaluations to assess long-term intervention effects. This outcome

measure is consistent with the symptom monitoring recommended by the national guidelines and has been suggested as a useful endpoint for pediatric asthma studies. Caregivers will be asked to report the number of days their child experiences *no* symptoms of asthma (defined as 24 hours with no coughing, wheezing, chest tightness, or shortness of breath) in the past 2 weeks. We will also assess asthma control with the Asthma Control Test.

**2. Healthcare Utilization:** Caregivers will report child's healthcare utilization at baseline and each follow-up. In addition, EHR data will be reviewed at each follow-up to assess for office visits (acute and routine), emergency department visits and hospitalizations. We will also evaluate healthcare utilization outcomes from the EHR data review for all patients with persistent or uncontrolled asthma (~5,000) across practices.

**3. Quality of Life:** Quality of life will be measured at baseline and each follow-up using Juniper's Pediatric Asthma Caregiver's Quality of Life Questionnaire (PACQLQ). The PACQLQ is a standard instrument used to assess the quality of life of caretakers of children with asthma, and provides a quantitative score that reflects answers to questions about the burden of caring for a child with asthma.

**4. Functional Severity:** Functional limitations of the child will be assessed at baseline and each follow-up evaluation using a subscale from the Children's Health Survey for Asthma. The child activity subscale includes 5 items on limitations to the child's activities due to asthma (Cronbach's alpha .87-.89).

**5. Beliefs about Medications and Adherence:** We will use the 10-item Horne's Beliefs about Medications Questionnaire (BMQ). Five questions assess parent's views about the necessity (alpha=.80) and five measure parental concern about their child's medications (alpha=.75). The 4-item Adherence Scale measures parent-reported medication adherence using a 5-point Likert scale (alpha=.60-.83).

### **Covariates:**

**1. Demographic Variables** will include child's age, gender, race, ethnicity, medical insurance, and caregiver's education level. We will use standardized questions from the national child health surveys to obtain these data.

**2. Medical Variables** will include birth history (prematurity), duration of asthma diagnosis and history of allergies (e.g., allergic rhinitis, seasonal allergies) or eczema.

**3. Caregiver Depression:** Caregiver depression has been shown to affect adherence to care plans, communication and child's asthma outcomes. We will assess maternal depression using a validated Patient Health Questionnaire 9 (PHQ-9).

Table 5. Measures	Measurement Strategy	Time of Administration
Clinical/Functional Outcomes		
Asthma Symptoms	Caregiver report on SFDs, ACT,  NHLBI guidelines 	Baseline; 3, 6, 9, & 12 months
Healthcare Utilization	Caregiver interview on health care contacts; EHR data	Baseline; 3, 6, 9, & 12 months; chart review
Quality of Life	Caregiver interview – Juniper Scale 	Baseline; 3, 6, 9, & 12 months
Functional Severity	Caregiver interview – Child Health Survey for Asthma 	Baseline; 3, 6, 9, & 12 months
Medication Beliefs/Adherence	Caregiver interview – Horne Scale 	Baseline; 3, 6, 9, & 12 months

SFDs=Symptom-Free Days; ACT=Asthma Control Test; EHR=Electronic Health Records

### **Potential Mediators:**

**1. Caregiver/Provider Communication:** We will use 5 communication items from the PACE Parent/Caregiver Questionnaire to assess caregiver's perception of their communication with the provider. Items are scored on a 6-point Likert scale (Don't know, Strongly Agree-Strongly Disagree).

**2. Self-Efficacy:** We will assess caregiver self-efficacy in communication with their child's provider using the validated Perceived Efficacy in Patient-Physician Interaction questionnaire (PEPPI).

**RE-AIM Measures:** We will use RE-AIM framework to evaluate the translational process: (1) the provider-level proportion of visits with corrective actions (*Reach*); (2) the impact of the intervention on provider delivery of guideline-based care (corrective actions taken at the visit) and SFDs (*Effectiveness*); (3) the pace and level of uptake of guidelines and changes in service utilization (*Adoption*); (4) improvements in reach and effectiveness over successive waves (*Implementation*); and (5) continued use of guidelines and sustainability of strategies by practices in order to facilitate dissemination to other clinical settings (*Maintenance*). We will be completing post-study qualitative interviews with approximately 125 clinic stakeholders (e.g. advisory board members, physicians, medical directors, nurses, and administrative personnel) from both eMPI and eUC practices to further evaluate the process of program implementation. Individual interviews will be completed through Zoom audio conference call, where clinic stakeholders will answer questions related to their clinic's culture, asthma management workflows, and barriers and facilitators to program implementation. The interviews will be audio-recorded and transcribed verbatim for further qualitative analyses.

**Analysis of qualitative data:** Transcribed interviews will be imported into the NVivo qualitative data software to assist with data organization. Qualitative data will be analyzed according to the concepts of grounded theory. Codebooks will be developed in an iterative fashion. Coders will independently code the first 3 transcripts, meet to compare codes, and then alter or add codes as necessary. After this, a codebook will be created to include definitions, rules, and examples for each code. The coders will then code all subsequent transcripts and revise the codebook as necessary to incorporate new codes or refine existing codes. The constant comparison method will be used to determine if there are any patterns or themes by provider/stakeholder characteristics.

